6.2 Control intervention

The control intervention will be placebo as described in section 3.3.

The intervention period will be identical to the intervention period of the experimental intervention.

6.3 Co-interventions

All patients in this trial will be offered co-interventions if indicated. Evidence regarding the use of sucralfate and antacids are weak [62] and we do not recommend the use of these drugs.

The registered co-interventions will be:

- any kind of mechanical ventilation (y/n) (daily)
- continuous treatment with vasopressor/inotropes (y/n) (daily)
- renal replacement therapy (y/n) (daily)
- number of units of red blood cells (daily)
- enteral nutrition (y/n) (daily)

ICU treatment and management in general will be at the discretion of the treating clinicians.

6.4 Concomitant interventions

PPI or H2RA cannot be prescribed as prophylaxis in the ICU during the intervention period. If the patient develops GI bleeding or another condition where treatment with one of the drugs is

indicted, the patient will be withdrawn from trial intervention and receive relevant treatment. Data collection will continue. If an included patient receives open-label PPI/H2RA (e.g. prescribed as prophylaxis) it will be considered a major protocol violation. This will be registered and the allocated trial intervention and data collection will be continued.

Previously randomised patients readmitted to the ICU:

- If the clinician finds indication to continue the PPI or H2RA prescribed in the ward, the trial medication will not be resumed, but data collection will continue
- If the clinician does not find indication to continue the PPI or H2RA prescribed in the ward, the drug will be discontinued and the allocated trial medication will be resumed

All other interventions will be allowed since they are expected to be distributed evenly in the two groups.

6.5 Intervention accountability

Pantoprazole for intravenous injection will be bought and delivered from Actavis to the Hospital Pharmacy of the Capital Region of Denmark. The pantoprazole will be part of the regular production and hence not made especially for the SUP-ICU trial. The Hospital Pharmacy will send it directly to Nomeco. Pharma-Skan ApS will produce the sterile empty vials used for placebo. The production will follow all regulations and according to Good Manufacturing Practice (GMP) and Good Distribution Practice (GDP). The vials will be delivered to Nomeco CTSM who will be responsible for storage, blinding, packaging and distribution of vials with pantoprazole 40 mg and empty vials (placebo) to national and international trial sites. All services will be performed by qualified and trained personnel and according to GMP and GDP

A computer program (from CTU) will generate a coding list with numbers for the vials. At randomisation, the computer program will allocate vials from the specific trial site to the patient. Nomeco CTSM will be responsible for having a sufficient number of vials to be allocated to patients enrolled at each trial site. At each trial site, trial products will be stored in a secure place. Combined with the unique packaging and labelling number this will ensure that trial medications will not be mixed up with other medications. Used and unused products will be registered.

7. Outcomes

All outcomes are defined in *appendix 4*.

7.1 Primary outcome

90-day mortality post-randomisation

7.2 Secondary outcomes

- Proportion of patients with one or more of the following adverse events: clinically important GI bleeding, pneumonia, CDI, or acute myocardial ischemia in the ICU
- Proportion of patients with clinically important GI bleeding in the ICU
- Proportion of patients with one or more infectious adverse events (pneumonia or CDI) in the ICU
- 1-year “landmark” mortality post-randomisation
- Days alive without the use of mechanical ventilation, renal replacement therapy or circulatory support in the 90-day period
- Number of SARs as defined in *appendix 4*
- A health economic analysis will be performed. The analytic details will be based on the result of the trial and specified (cost-benefit vs cost-minimisation analyses)

The specific elements of the composite outcomes will be reported in supplementary material to the primary publication.

7.3 Exploratory outcomes

No exploratory outcomes or sub-studies are planned. However, sub-studies will be encouraged as long as they don't hamper the completion of the main protocol and can be conducted after approval of the protocol by the Steering Committee (SC).

8. Safety

8.1 Definitions

Adverse event (AE): any undesirable medical event occurring to a patient during a clinical trial, which does not necessarily have a causal relationship with the intervention.

Adverse reaction (AR): any undesirable and unintended medical response related to the intervention occurring to a patient during a clinical trial. Adverse reactions are specified in the product characteristics of pantoprazole (see *appendix 2* and *5*)

Serious adverse event (SAE): any adverse event that results in death, is life-threatening, requires hospitalization or prolongation of existing hospitalization, results in persistent or significant disability or incapacity.

Serious adverse reaction (SAR): any adverse reaction (as defined above) that results in death, is life-threatening, requires hospitalization or prolongation of existing hospitalization, results in persistent or significant disability or incapacity.

Suspected unexpected serious adverse reaction (SUSAR): any suspected adverse reaction which is both serious and unexpected. SUSARs will be defined as serious reactions not described in the summaries of product characteristics for pantoprazole.

8.2 Risk and safety issues in the current trial

Pantoprazole is well tolerated and most adverse reactions have been mild and transient showing no consistent relationship with treatment. Approximately 5% of patients can be expected to experience adverse drug reactions. The most commonly reported are diarrhoea and headache, both occurring in approximately 1% of patients. Because of intravenous administration, there will be a risk of phlebitis in both groups.

In *appendix 2* all adverse reactions for pantoprazole are listed.

Apart from the risk of phlebitis, there is no risk of adverse reactions to the placebo (10 ml of isotonic saline).

See Summary of Product Characteristics in *appendix 5*.

8.3 Serious adverse reactions and events

SARs to pantoprazole:

Registered SARs are defined in *appendix 4* and ARs not registered are discussed in *appendix 6*.

SARs to 10 ml of isotonic saline:

No SARs are associated with such small amount of intravenous isotonic saline.

8.3.1 Recording of serious adverse reactions and events

SARs will be recorded daily in the eCRF from the time of the first administration of trial medication and until 24 hours after last administration of trial medication or the patient is discharged from the ICU. If the patient is readmitted to the ICU and trial medication is re-introduced, SARs will be recorded. When a SAR is registered in the eCRF the coordinating investigator will be informed directly which will secure fast reporting of SAR. SARs in the two groups will be compared in the interim analyses and as an outcome measure. If a patient experiences a SAR he or she will be withdrawn from the trial. Daily registration will be continued and the follow-up will be conducted.

If a patient experiences SUSAR, the local investigator must report this without undue delay to the Sponsor (or delegated party). The patient will be withdrawn from the trial and the trial medication will be demasked. If a SUSAR is still reasonable after demasking, a report will be conducted describing onset and end of event, severity, the relation to the intervention, the actions taken and the outcome.

SAEs will not be recorded as an entity, because the majority of ICU patients will experience several SAEs during their critical illness. The most important SAEs will be captured in the secondary outcome measures (days alive without life-support). Patient charts, notes and lab reports will contain daily registrations of clinical data, which can be obtained on request from the medical authorities.

8.4 Reporting

Trial investigators are to report SUSARs without any delay to the sponsor, which in turn will report these to the Danish Health and Medicine Authorities 7 days at the latest after the report has been received.

9. Procedures, assessments and data collection

9.1 Inclusion procedure

9.1.1 Screening

All patients admitted to participating ICUs will be eligible for screening. In fertile women a negative urine-hCG or plasma-hCG must be present before enrolment.

9.1.2 Procedures for informed consent

Patients will be enrolled after consent is obtained according to national regulations. This procedure will be described by each participating country. The procedure for Danish patients is described in *appendix 7*.

9.2 Data collection

9.2.1 Method

Data will be obtained in eCRFs from a combination of patient files and national registers. For patients transferred from a trial ICU to a non-trial ICU, data related to the outcomes of interest will be collected after transferral e.g. by national registers, phone calls, and patient charts.

9.2.2 Timing

Appendix 8 shows an overview of the timing and all variables are defined in *appendix 4*.

Baseline variables (not collected in the screening procedure)

- Sex
- Age at randomisation/date of birth
- Date of admission to hospital and date and time to ICU
- Elective or emergency surgery during current hospitalization (y/n)
- Treatment of suspected or confirmed CDI during current hospital admission (y/n)
- Treatment with NSAID or acetylsalicylic acid at hospital admission (y/n)
- Treatment with anticoagulants at hospital admission (y/n)
- Intravenous thrombolysis within the previous 3 days (y/n)
- Co-morbidities (see definitions in *appendix 4*):
 - history of chronic lung disease
 - history of myocardial ischemia
 - history of severe chronic heart failure (NYHA 3-4)

- history of chronic renal failure in the last year prior to hospital admission
- treatment with at least 0.3 mg/kg/day of prednisolone equivalent for at least one month in the 6 month prior to ICU admission
- active hematologic cancer
- metastatic carcinoma
- AIDS
- Values for simplified acute physiology score (SAPS) II 24 hours prior to randomisation (not covered above): heart rate, systolic blood pressure, core temperature, PaO₂/ FiO₂ ratio, urinary output, urea, white blood cell count, potassium, sodium, bicarbonate, bilirubin, Glasgow Coma Scale (GCS) score (*appendix 9*)
- Variables for severity organ failure assessment (SOFA) scoring 24 hours prior to randomisation not covered in SAPS II scoring: blood platelets, MAP, dose of noradrenalin, adrenalin and dopamine, use of inotropes, plasma creatinine (*appendix 10*)

Daily during ICU admission:

- Delivery of trial medication (y/n)
- Open label treatment with PPI/H₂RA (y/n)
- Invasive or non-invasive mechanical ventilation (y/n)
- Circulatory support (infusion of vasopressor/inotropes) (y/n)
- Any form of renal replacement therapy (y/n)
- Onset of pneumonia (as defined in *appendix 4*) on this day (y/n)
- Treatment with antibiotics (enteral vancomycin, intravenous or enteral metronidazole, or enteral fidaxomicin) for suspected or proven CDI on this day (y/n)
- Acute myocardial ischemia (as defined in *appendix 4*) on this day (y/n)
- Enteral feeding on this day (y/n)
- Number of units of RBCs
- Overt bleeding episodes (hematemesis, coffee ground emesis, melena, hematochezia or bloody nasogastric aspirate) (y/n)
- SARs (y/n) (*appendix 4*)

Bleeding form (only for patients with overt bleeding)

- Data on clinically important bleeding (overt GI bleeding as defined above and at least one of the following four features within 24 hours of GI bleeding (in the absence of other causes) in the ICU:
 - a spontaneous drop of systolic blood pressure, mean arterial pressure or diastolic blood pressure of 20 mmHg or more
 - start of vasopressor or a 20% increase in vasopressor dose
 - decrease in haemoglobin of at least 2 g/dl (1.24 mmol/l)
 - transfusion of 2 units of packed red blood cells or more
- Origin of GI bleeding confirmed (y/n)
- Verification of ulcer/gastritis/esophageal varices (y/n)
- Haemostasis achieved/attempted by endoscopy/open surgery/coiling (y/n)

Follow-up 90 days after randomisation

- Death (y/n, if yes, date of death)

Follow-up 1 year after randomisation

- Death (y/n, if yes, date of death)

10. Data handling and record keeping

10.1 Data management

Data will be entered into an electronically, web-based eCRF from medical files and national registers by trial personnel.

10.2 Confidentiality

Each patient will receive a unique trial identification number. Trial investigators will receive personal username and passwords to access the randomisation system and the eCRF. Each site will only have access to site specific data.

Data will be handled according to the National Data Protection Agency, and is protected by the Danish national laws 'Loven om behandling af personoplysninger' and 'Sundhedsloven'.

10.3 Biobanking

No biobank will be formed.

10.4 Access to data

All original records (incl. consent forms, eCRFs, and relevant correspondences) will be archived at trial sites for 15 years. The clean electronic trial database file will be delivered to the Danish Data Archive and maintained for 15 years and anonymised if requested by the authorities.

11. Statistical analysis

90-day mortality and 1-year mortality have been chosen as outcomes for all-cause mortality. Besides landmark mortality, mortality 90 days and 1 year after last randomised patient have been considered, but due to practical and organisational matters, and lack of centralised registration, it will be difficult and for some countries impossible to get mortality data up to 3 years after enrolment of a patient.

11.1 Sample size estimation and power calculations

11.1.1 Sample size estimation for the primary outcome

Primary outcome measure

Assuming a baseline 90-day mortality of 25% [9] (see *appendix 11*) $\alpha=0.05$ (two-sided), and $\beta=0.1$, 3350 patients (2 x 1675) will be needed to show a 20% relative risk reduction (RRR) or increase (RRI) corresponding to a 5% absolute risk reduction or risk increase in the primary outcome measure.

Trial Sequential Analysis [63, 64] of existing trials ($n=16$) has showed that 35% (1584 patients) of the required information size to detect or reject a 20% RRR corresponding to 4,575 patients has been accrued [31]. Consequently, there is an information gap of around 3000 patients assuming a 20% RRR in mortality (*appendix 12*). With the inclusion of an additional 3350 patients it is expected that the pooled effect will cross the boundary for benefit/harm or the boundary for futility.

11.1.2 Power estimations for secondary outcomes

Power estimations are based on 3350 included patients, a risk of type 1 error of 5%, and a minimal clinically relevant difference as stated:

Clinically important GI bleeding: 46% power (baseline 3% -> 2% = 33% RRR) for showing or discarding a numbers-needed-to-treat (NNT) of 100.

Pneumonia: 85% power (baseline 20% -> 16% = 20% RRR) for showing or discarding a NNT of 25.

CDI: 53% power (baseline 10% -> 8% = 20% RRR) for showing or discarding a NNT of 50.

Myocardial ischemia: 29% power (baseline 5% -> 4% = 20% RRR) for showing or discarding a NNT of 100

11.2 Statistical methods

The primary analysis will be conducted including the intention-to-treat population [65–67]. A sensitivity analysis will be conducted including the per-protocol population, excluding patients with a major protocol violation (patients who did not receive the allocated trial intervention at all, patients who did not receive the trial intervention for at least two days in a row, treatment with PPI or H2RA without clinically indication and withdrawal from trial intervention). Patients transferred to another ICU will be considered discharged from the ICU.

The primary analysis of all dichotomous outcomes will compare the outcome at 90 days after randomisation in the two groups by binary logistic regression analysis with adjustment for stratification variables [68]: site and active haematological cancer

A secondary analysis will be performed adjusting for stratification variables together with other known major prognostic co-variables: age, baseline SOFA score, and type of admission (medical, elective surgery or emergency surgery).

Further details will be provided in a statistical analysis plan.

11.2.1 Pre-planned subgroup analyses

We will compare the primary outcome measure in pre-specified subgroups defined according to 1) shock at randomisation (y/n), 2) mechanical ventilation at randomisation (y/n), 3) coagulopathy at randomisation or history of coagulopathy (y/n), 4) history of liver disease (y/n) 5) type of ICU admission (medical/surgery) and 6) SAPS II > 53 points (y/n).

11.2.2 Significance

A two-sided P value of less than 0.05 will be considered statistically significant.

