11.2.3 Interim analysis

Interim analyses will be conducted after patient no. 1650 and 2500 has been followed for 90 days.

The DMSC will constitute its own plan of monitoring and meetings. The charter for the independent Data Monitoring and Safety Committee (DMSC) (*appendix 3*) defines the minimum of obligations and primary responsibilities of the DMSC as perceived by the SC, its relationship with other trial components, its membership, and the purpose and timing of its meetings.

The DMSC may recommend pausing or stopping the trial if group-difference in the primary outcome measure, SARs or SUSARs are found at the interim analyses with statistical significance levels adjusted according to the LanDeMets group sequential monitoring boundaries based on O'Brien Fleming alpha-spending function [69]. If an analysis of the interim data from 1650/2500 patients fulfils the LanDeMets stopping criterion the inclusion of further patients will be paused and an analysis including patients randomised during the analysis period will be performed. If this second analysis also fulfils the LanDeMets stopping criterion according to the group sequential monitoring boundaries the SC may stop the trial [67]. Furthermore, the DMSC can recommend pausing or stopping the trial if continued conduct of the trial clearly compromises patient safety. However, stopping for futility to show an intervention effect of 15% RRR will not be an option as intervention effects less than 15% RRR of all-cause mortality may be clinically relevant as well.

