Interim analyses will be conducted after patient no. 1650 and 2500 has been followed for 90 days. The DMSC will recommend pausing or stopping the trial if group-difference in the primary outcome measure, SARs or SUSARs are found at the interim analyses with statistical significance levels adjusted according to the LanDeMets group sequential monitoring boundaries based on O'Brien Fleming alpha-spending function [69]. If an analysis of the interim data from 1650/2500 patients fulfils the LanDeMets stopping criterion the inclusion of further patients will be paused and an analysis including patients randomised during the analysis period will be performed. If this second analysis also fulfils the LanDeMets stopping criterion according to the group sequential monitoring boundaries the DMSC will recommend stopping the trial [67]. Furthermore, the DMSC can recommend pausing or stopping the trial if continued conduct of the trial clearly compromises patient safety. However, stopping for futility to show an intervention effect of 15% RRR will not be an option as intervention effects less than 15% RRR of all-cause mortality may be clinically relevant as well.

This recommendation will be based primarily on safety and efficacy considerations and will be guided by statistical monitoring guidelines defined in this charter and the trial protocol.

The SC is jointly responsible with the DMSC for safeguarding the interests of participating patients and for the conduct of the trial. Recommendations to amend the protocol or conduct of the trial made by the DMSC will be considered and accepted or rejected by the SC. The SC will be responsible for deciding whether to continue, hold or stop the trial based on the DMSC recommendations.

The DMSC will be notified of all changes to the trial protocol or conduct. The DMSC concurrence will be sought on all substantive recommendations or changes to the protocol or trial conduct prior to their implementation.

Statistical monitoring guidelines

The outcome parameters are defined in the statistical analyses plan in the protocol. For the two intervention groups, the DMSC will evaluate data on:

The primary outcome measure

Mortality 90 days after randomisation of each patient (“landmark mortality”).

The secondary outcome measures

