Because of the widespread use of SUP, no reliable control group for sample size estimation is available and producing reliable sample size estimations according to anticipated effects on GI bleeding is difficult.¹ As a consequence it has been necessary to calculate sample size estimations given that something may change if we withhold PPI until GI bleeding actually happens. Assuming a baseline 90-day mortality of 25%,² $\alpha=0.05$ (two-sided), and $\beta=0.1$, 3350 patients (2 x 1675) will be needed to show a 20% relative risk reduction (RRR) or increase (RRI) corresponding to a 5% absolute risk reduction or increase in the primary outcome measure. Trial Sequential Analysis^{22,23} of existing trials (n=16) has showed that 35% (1584 patients) of the required information size to

detect or reject a 20% RRR or RRI corresponding to 4575 patients has been accrued.⁸

Consequently, there is at least an information gap of around 3000 patients taking a 20% RRR in mortality as a clinically relevant effect size.

Outcome measures

Primary outcome

The primary outcome measure is all-cause mortality within 90 days after randomisation.

Secondary outcomes

1. Proportion of patients with one or more episodes of clinically important GI bleeding, pneumonia, *Clostridium difficile* infection or myocardial ischemia. The events are defined in appendix 1
2. Proportion of patients with one or more episodes of clinically important GI bleeding
3. Proportion of patients with one or more infectious adverse events (pneumonia or *Clostridium difficile* infections)
4. All-cause mortality within 1 year after randomisation
5. Percentage of days alive without use of life support (mechanical ventilation, circulatory support or renal replacement therapy) in the 90-day period
6. The number of patients with one or more serious adverse reactions (SARs) (defined in appendix 2)
7. A health economic analysis will be performed. The analytic details will be based on the result of the trial and specified prior to the analysis.

Pre-planned subgroup analyses

The primary outcome measure will be compared in the following pre-specified subgroups (definitions provided in appendix 2)

1. Shock at randomisation (y/n) (a hypothesised increased intervention effect in patients with shock at randomisation)
2. Mechanical ventilation at randomisation (y/n) (a hypothesised increased intervention effect in patients mechanically ventilated at randomisation)

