If multiple imputation is used, the primary result of the trial will be based on these data. A 'best-worst, worst-best case' scenario will be used as a sensitivity analysis to assess the potential impact of any pattern of missingness including that the data are missing not at random (MNAR criterion) for the trial results. In the 'best-worst-case' scenario it is assumed that all patients lost to follow-up in the experimental group have had a beneficial outcome (e.g. have survived) and all those with missing outcomes in the control group have had a harmful outcome (e.g. have not survived). Conversely, in the 'worst-best-case' scenario, it is assumed that all patients who were lost to follow up in the experimental group have had a harmful outcome; and that all those lost to follow-up in the control group have had a beneficial outcome.

The unadjusted, non-imputed analysis will also be presented.

General analytic principles

1. All main analyses will compare the two intervention groups in the intention-to-treat (ITT) population.²⁴⁻²⁶

The ITT population will be all patients randomised except:

- patients withdrawing consent for the use of data
- patients who were erroneously randomised AND who did not receive the trial intervention.²⁷

The conclusion of the trial will be based on the ITT analysis

2. In all analyses, a maximum level of 5% (two-sided) type 1 error will be regarded as statistically significant
3. Test-of-interaction will be applied for all subgroup analyses (logistic regression)

Statistical analyses

Trial profile

The flow of trial participants will be displayed in a Consolidated Standards of Reporting Trials (CONSORT) diagram. The number of participants fulfilling the inclusion criteria, the number of excluded participants and reasons for exclusion, and the number of participants included in the final analyses will be presented.

Primary outcome measure

The primary analysis will be a logistic regression analysis adjusted for stratification variables (site and presence of haematological cancer, y/n) of the ITT population. Results will be presented as odds ratios and relative risk ratios (relative risk ratios computed from odds ratios with covariates set to mean values for numeric covariates and the largest group for categorical).

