Based on evaluation of these outcomes, the DMSC will decide if they want further data from the coordinating centre and when to perform the next analysis of the data. Additionally, the DMSC will yearly be informed about SARs occurring in the two groups of the trial. The interim analyses will be performed by an independent statistician selected by the members of the DMSC. The DMSC can, at any time during the trial, request the distribution of events, including outcome measures and SARs according to intervention groups. Further, the DMSC can request unblinding of the interventions. The DMSC may recommend pausing or stopping the trial if group-difference in the primary outcome measure, SARs or Suspected Unexpected Serious Adverse Events (SUSARs) are found in the interim analyses with statistical significance levels adjusted according to the LanDeMets group sequential monitoring boundaries based on O'Brien Fleming alpha-spending function.³⁰ If an analysis of the interim data from 1650 or 2500 patients fulfils the LanDeMets stopping criterion the inclusion of further patients will be paused and an analysis including patients randomised during the analysis period will be performed. If this second analysis also fulfils the LanDeMets stopping criterion according to the group sequential monitoring boundaries the Steering Committee may stop the trial.²⁶ Furthermore, the DMSC can recommend pausing or stopping the trial if continued conduct of the trial clearly compromises participant safety. However, stopping for futility to show an intervention effect of 15% RRR or RRI will not occur, as intervention effects less than 15% RRR or RRI in all-cause mortality may be clinically relevant as well.

Ethical approval and Consent to participate

The SUP-ICU trial has been registered on www.clinicaltrials.gov (NCT02467621), the trial is approved by the Danish Health and Medicine Agency (2015030166), the Committees on Health Research Ethics in the Capital Region of Denmark (H-15003141) and by the Danish Data Protection Agency (RH-2015-3203695).

Additionally, the trial is approved by the following ethical committees:

Norway: Regionale Komiteer for Medisinsk og Helsefaglig Forskningsetikk (2015/1490/REK vest)

Finland: Tutkimuseettinen toimikunta (372/2015)

The Netherlands: Medisch Ethische Toetsingscommissie (M15.182376)

Switzerland: Kantonale Ethikkommission Bern (205/15)

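### Protocol 11.2.2 sets P<0.05 with no exception for the final primary test although alpha is spent at an interim look, and no final level is stated (minor)

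*Combined protocol and SAP*

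**What the plan says.** Protocol 11.2.2 (same text in both copies of the protocol): "A two-sided P value of less than 0.05 will be considered statistically significant". Nothing else stands in that section.

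SAP, General analytic principles, item 2: "In all analyses, a maximum level of 5% (two-sided) type 1 error will be regarded as statistically significant".

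Protocol 11.2.3 lets the DMSC recommend pausing or stopping if a "group-difference in the primary outcome measure, SARs or SUSARs are found at the interim analyses with statistical significance levels adjusted" by Lan-DeMets boundaries with O'Brien-Fleming spending. The charter (Appendix 3.1) uses nearly the same words. The SAP, under Interim analysis, refers to differences that "are found in the interim analyses with statistical significance levels adjusted according to the LanDeMets group sequential monitoring boundaries". All three attach the adjusted levels to the interim analyses. None gives a level for the final analysis.

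A crossing does not stop the trial by itself. Recruitment is paused and the analysis is repeated with the patients randomised meanwhile. The SAP then says: "If this second analysis also fulfils the LanDeMets stopping criterion according to the group sequential monitoring boundaries the Steering Committee may stop the trial".

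Appendix 3.1 (Amendment 3, June 2017) cancels the look at 2500 patients and reports the first look at 1675 of 3350. It does not restate a final level. The SAP and the charter also say that, after seeing the outcomes, "the DMSC will decide if they want further data from the coordinating centre and when to perform the next analysis of the data".

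**The concern.** A spending function divides one 5% among all analyses, the last included. Whatever is spent at the interim is no longer available at the end, so the final critical value must lie slightly above 1.96. Protocol 11.2.2, followed as written, puts it at 1.96 and uses the interim portion twice.

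Two things follow. The overall error is slightly above the 5% that the plan states. There is also a narrow band of final P values in which 11.2.2 and the plan's own spending function disagree: a final P of 0.0495 would be significant under the first and not under the second. Since this is the decision threshold for the primary outcome, it should be settled before the groups are unmasked.

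**Working it through.** **Inputs.** Total 3350 (2 x 1675), mortality 25% versus 30%, two-sided alpha 0.05, power 90% (protocol 11.1.1). Interim look at 1675, t = 1675/3350 = 0.50 (Appendix 3.1); planned at 1650, t = 0.4925 (protocol 11.2.3). The number of patients added before the confirming analysis is not given; I assume 100, 300 and 600.

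**1. The plan's own sample size.** With a pooled rate of 0.275,
n = [1.960 x sqrt(2 x 0.275 x 0.725) + 1.2816 x sqrt(0.25 x 0.75 + 0.30 x 0.70)]^2 / 0.05^2 = (1.2377 + 0.8080)^2 / 0.0025 = 1674 per group. The plan states 1675, so it is a fixed-design calculation at the full 0.05, with no sequential adjustment.

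**2. Alpha spent at the look.** The plan names the function but not its form.
- Two one-sided 0.025 functions: alpha(t) = 4[1 - Phi(2.2414/sqrt t)]. At t = 0.50 this is 0.00305, so the interim z is 2.963.
- One two-sided 0.05 function: alpha(t) = 2[1 - Phi(1.960/sqrt t)]. At t = 0.50 this is 0.00557, so the interim z is 2.772.

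**3. Final boundary.** Solve P(|Z1| < c1, |Z| < c) = 0.95, where Z1 and Z have correlation sqrt t. The last column is the overall error if the final test uses 1.960 instead and one interim crossing counts as rejection.

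| Form | Look | Interim z | Final z | Final P | Matching CI | Overall error at 0.05 |
|---|---|---|---|---|---|---|
| Two one-sided | 1650 | 2.988 | 1.968 | 0.0491 | 95.09% | 5.09% |
| Two one-sided | 1675 | 2.963 | 1.969 | 0.0490 | 95.10% | 5.10% |
| Single two-sided | 1650 | 2.793 | 1.978 | 0.0479 | 95.21% | 5.20% |
| Single two-sided | 1675 | 2.772 | 1.979 | 0.0478 | 95.22% | 5.22% |

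The choice between 1650 and 1675 moves the final P by 0.0001; the form moves it by about 0.001.

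**4. The rule the plan actually uses.** If the criterion must be met twice, then
overall error = 0.05 + 2 P(Z1 > c1, Z2 > c2, |Z| < 1.960),
where c2 is the boundary at the confirming analysis. I set c2 either recursively or from the cumulative spending alone, since the plan does not say which. With 100 to 600 added patients and a look at 1650 or 1675, the results are:
- two one-sided functions: 5.04% to 5.07%;
- single function: 5.08% to 5.15%.

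Allowing 0.01 points at the upper ends for other ways of setting c2 gives 5.08% and 5.16%. The fact that stopping is discretionary can only lower these figures.

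**5. Power at the corrected boundary.** Power = Phi(0.05/sqrt(0.3975/1675) - z) = Phi(3.246 - z).
- z = 1.960: 90.1%.
- z = 1.969: 89.9%.
- z = 1.979: 89.7%.

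**The case against.** The best defence is that 11.2.2 is a one-line convention that does not name the final primary analysis, and that the protocol leaves analytic detail to the SAP. The SAP's rule is a maximum type 1 error, which can be read as an overall cap. With that cap and a named spending function, the final boundary follows from the looks taken once the form is known. Naming the function in advance is the core of the pre-specification, and no fixed number could have been printed before the schedule was settled. Much of this stands. It does not close the point, because the cap gives no final level and does not override the flat threshold in 11.2.2. Under the cap reading the two texts disagree.

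It is also fair that 5.1% to 5.2% describes a rule the plan does not use. Because the criterion must be met twice and stopping is discretionary, those figures are ceilings.

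A reader might go further in two ways that the documents do not support:

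- Because protocol 11.2.3, the charter and the SAP still list a look at 2500 patients, a reader might infer a larger excess from that look or a later one. Appendix 3.1 cancels the second look because its 90-day results would come only after the trial was completed. A look that late could not act as an interim look. The DMSC may still choose to look again, but no further look is scheduled.
- SARs share the interim boundaries and return as a final secondary outcome ("The number of patients with one or more serious adverse reactions (SARs"). A reader might infer that their final test must be tightened too. For SARs the boundary serves as a safety trigger. The documents give no basis for sizing any error there, and a stricter level would make a harm signal harder to declare.

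**Conclusion.** The point holds, and it is minor. Followed as written, protocol 11.2.2 gives an overall two-sided error of about 5.04% to 5.08% with two one-sided spending functions, and up to about 5.16% with a single two-sided function. The excess is therefore roughly 0.04 to 0.16 percentage points. The ceiling, if one crossing counted as rejection, is 5.1% to 5.2%.

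These figures assume one formal look at 1650 or 1675 of 3350, no further comparative look, and 100 to 600 patients added before the confirming analysis. They do not show that the plan abandons error control, because the SAP's cap points the other way. They show that the stated threshold and the spending function do not meet, and that the gap changes the conclusion only for a final P between about 0.048 or 0.049 and 0.05.

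**What to change.** Amend protocol 11.2.2 and SAP principle 2 to say:

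- The primary outcome is tested at the final Lan-DeMets boundary with O'Brien-Fleming spending, for the looks and information fraction actually used.
- Which form applies. For one look, two one-sided 0.025 functions give a final P of about 0.049 and a CI of about 95.1%; one two-sided 0.05 function gives about 0.048 and 95.2%.
- The matching confidence interval is reported for the primary outcome.
- Any further comparative look by the DMSC enters the boundary.

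This costs a few words in each document and at most about 0.3 points of power. Sample size and data collection do not change.
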